## **9.5. Clinical Laboratory Evaluations**

Laboratory parameters will be summarized in the standard international system of units. Quantitative laboratory results will be summarized using descriptive statistics at baseline and at each post-baseline scheduled visit. Both absolute and percentage change from baseline will also be summarized.

### **9.5.1. Shifts in Normal Range**

Shift tables (ie, low-normal-high at baseline versus low-normal-high at post-baseline visit in a 3 by 3 contingency table) from baseline to worst value (including scheduled or unscheduled) and last value (including scheduled and unscheduled) will be provided for hematology, serum chemistry, quantitative urinalysis, and lipids. For urinalysis parameters, a shift table depicting shifts to/from positive/negative from baseline to worst and last value will be provided.

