- c Vital signs should be measured prior to having blood drawn for laboratory evaluations. BP will be measured after participants have been sitting comfortably in a chair for at least 5 minutes prior to obtaining 3 readings using the same arm for each reading; the mean of the last 2 readings will then be recorded. Weight, heart rate, temperature, respiration rate, and height (height measured only at screening) will also be recorded.
- d Includes clinical chemistry (serum sodium, potassium, chloride, bicarbonate, total protein, albumin, calcium, phosphate, glucose, cystatin, uric acid, BUN, creatinine [including calculation of eGFR], bilirubin [total, direct, and indirect], ALT, AST, ALP, gamma glutamyl transferase, creatine kinase, and amylase); hematology (red blood cells, hemoglobin, hematocrit, MCV, MCH, MCHC, platelets, WBC, and WBC differential [percentage and absolute] neutrophils, eosinophils, basophils, lymphocytes, and monocytes); and routine urinalysis (color, appearance, and dipstick [pH, specific gravity, protein, glucose, ketones, bilirubin, blood, urobilinogen, and leukocyte esterase]). All chemistry and hematology analytes are shown in [Section 10.3](#).
- e Includes total cholesterol, LDL (direct), HDL (direct), and triglycerides (direct). All lipid analytes are shown in Section 10.3.
- f Full physical examination will be performed at screening. A symptom directed targeted physical examination will be performed for all other visits.
- g After Week 24/EOT, participants are expected to restart SOC treatment. The restart of RAAS inhibitor is at the discretion of the Investigator.
- h The day before visit, participants should avoid strenuous exercise and a high protein meal, and participants should maintain a stable water intake.
- i At screening, serum pregnancy tests will be performed on participants who can become pregnant. Urine pregnancy tests will be performed at all other visits and monthly between visits. A positive urine pregnancy test will be confirmed by a serum test.
- j Sites will provide participants who can become pregnant with enough tests to conduct pregnancy testing once per month until the next scheduled study visit and will contact these patients monthly to confirm that the pregnancy test has been performed and the results are negative.

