2. INTRODUCTION

Immunoglobulin A nephropathy (IgAN), also known as Berger's disease, is a form of glomerulonephritis originally described in 1968. Although the pathogenesis of IgAN has not been elucidated, several lines of evidence indicate that it is an autoimmune disease with an extrarenal etiology (Knoppova 2016). IgAN is a serious, progressive disease in which 20% to 40% of patients progress to kidney failure (KF) within 10 to 20 years of diagnosis (Manno 2007; Berthoux 2011; Moriyama 2014). As most patients are diagnosed in their 20s or 30s, they face the prospect of dialysis or the need for kidney transplantation in the prime of their lives. Geddes et al (Geddes 2003) conducted a retrospective analysis of patients with IgAN across 4 countries on 3 continents (Europe, North America, and Australia) to assess long-term outcome of the disease. From first clinical presentation, the overall 10-, 15-, and 20- year actuarial renal survival rates were 77.8%, 69.8%, and 55.3%, respectively. Due to the extrarenal etiology of IgAN in which the kidney is the end organ damaged by a systemic immunological condition, the incidence of IgAN recurrence following kidney transplantation is high; when posttransplant biopsies were routinely collected (regardless of symptomology), the recurrence of IgAN has been reported in 50% to 60% of patients, with an estimated 10-year incidence of graft loss due to recurrence of approximately 10% (Choy 2006).

Patients with IgAN typically present in 1 of 3 ways (Donadio 2002b; Galla 1995). Approximately 40% to 50% of patients present with 1 or recurrent episodes of visible hematuria, usually following an upper respiratory tract infection; these patients are not considered to be at risk for progression to KF. Less than 10% of patients present with nephrotic syndrome or acute, rapidly progressing glomerulonephritis and, in rare cases, may present with malignant hypertension. The remaining 30% to 40% of patients have persistent proteinuria that may be accompanied by microscopic hematuria, which is detected incidentally upon routine examination (Hall 2004; Topham 1994); this group is the target patient population for treatment with sparsentan and is addressed by the Kidney Disease Improving Global Outcomes (KDIGO) Clinical Practice Guideline for Glomerulonephritis (KDIGO 2021).

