5.1. Inclusion Criteria

Participants are eligible to be included in the study only if all the following criteria apply:

Informed Consent

Capable of giving signed informed consent as described in Appendix 1 which includes compliance with the requirements and restrictions listed in the ICF and in this protocol.

Age

1. Participant must be ≥ 18 years of age inclusive, at the time of signing the informed consent.

Type of Participant and Disease Characteristics

2. Participant has biopsy-proven IgAN. The biopsy may have been performed at any time in the past.
3. Participant has a UA/C ≥ 0.3 g/g at screening.
4. Participant has an eGFR value of ≥ 25 mL/min/1.73 m² at screening

Contraceptive/Barrier Requirements

5. Participants who can become pregnant, must agree to the use of 1 highly reliable (ie, can achieve a failure rate of <1% per year) method of contraception from 7 days prior to the first dose of study intervention until 30 days after the last dose of study intervention. Highly reliable contraception methods include stable oral, implanted, transdermal, or injected contraceptive hormones associated with inhibition of ovulation, or an intrauterine device (IUD) in place for a duration defined as effective in product labeling. If hormonal contraception is used, one additional barrier method must also be used during sexual activity, such as a diaphragm or diaphragm with spermicide (preferred), or male condom or male condom with spermicide (preferred), from Day 1/Randomization until 30 days after the last dose of study intervention. Hormonal implants do not require an

additional barrier method to be used. Participants who can become pregnant are defined as those who are fertile, following menarche and until becoming postmenopausal unless permanently sterile; permanent sterilization methods include hysterectomy, bilateral salpingectomy, and bilateral oophorectomy. A postmenopausal state is defined as amenorrhea for more than 12 consecutive months without an alternative medical cause; participants on hormone replacement therapy must have a documented plasma follicle stimulating hormone level >40 mIU/mL. All participants who can become pregnant must have a negative serum pregnancy test at screening (Visit 1), and a negative urine pregnancy test, with positive results confirmed by serum, at every study visit from baseline (Visit 2) and after. See [Section 10.7](#) for additional details on contraceptive and barrier guidance.

Other Inclusion Criteria

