#### **3.2.2. Safety Endpoints**

Safety endpoints include the following:

- The incidence of treatment-emergent adverse events (TEAEs), serious adverse events (AEs), AEs leading to treatment discontinuation, and adverse events of interest (AEOI).
- Changes from baseline in body weight, vital signs, physical examinations, peripheral edema, and clinical laboratory parameters.

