## 7.4. Demographic and Baseline Characteristics

Demographic variables will include the following:

- Age (at informed consent)
- Sex
- Race
- Ethnicity

Other baseline characteristics will include the following:

- Weight (kg)
- Height (cm)
- Body mass index (kg/m^2)
- BP (systolic and diastolic)
- Childbearing potential (for females only)

- Hemoglobin A1c (%)
- Blood glucose (mmol/L)
- Glycosuria (Urine glucose values of “Trace”, ‘1+’, ‘2+’, ‘3+’, ‘Present’, etc)
- Hematuria (Urine Blood/Hgb values of “Trace”, ‘1+’, ‘2+’, ‘3+’, ‘Present’, etc)
- UA/C
- eGFR (mL/min/1.73 m^2), continuously and including the following categories:
  - <25 mL/min/1.73 m^2, ≥25 to <60 mL/min/1.73 m^2, ≥60 mL/min/1.73 m^2
  - <15 mL/min/1.73 m^2, ≥15 to <30 mL/min/1.73 m^2, ≥30 to <45 mL/min/1.73 m^2, ≥45 to <60 mL/min/1.73 m^2, ≥60 to <90 mL/min/1.73 m^2, ≥90 mL/min/1.73 m^2
- UP/C (g/g), continuously and including the following category.
  - ≤1.25 g/g, >1.25 g/g
- Current RAASi at Screening and at Day -1
  - Any RAASi
  - RAASi at maximum labeled dose (MLD)
  - ACEI at MLD
  - ARB at MLD
  - ACEI and ARB at MLD
  - ACEI or ARB at MLD
- Baseline concomitant medication use\*
  - Antihypertensive medications, lipid-lowering medications, Immunosuppressive agents with renal indication (ie, steroids, calcineurin inhibitors, mycophenolate mofetil and other immunosuppressive agents). Renal indication will be determined via medical review of concomitant medications and associated indications.

\* Medication lists will be reviewed and documented prior to the database lock to finalize the list of medications to be included in each category.

Demographics and baseline characteristics will be summarized and presented for both the FAS and PPAS. All baseline characteristics will use the last available data prior first dose of study medication except UA/C and UP/C will use the definition described in [Section 6.4.2](#). A by-patient listing will also be provided.

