## **8.2.3. Exploratory Efficacy Endpoints**

### **8.2.3.1. Continuous Endpoints**

Quantitative urinalysis parameters (protein excretion, albumin excretion, urea, and creatinine) will be summarized and analyzed similarly to UA/C as described in Section 8.2.1).

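### The SAP's positive/negative shift table for dipstick urinalysis hides graded change in urine blood among participants already positive at baseline, and no other planned tabulation clearly shows it

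*SAP*

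**What the plan says.** Dipstick urinalysis belongs to the clinical laboratory assessments scheduled at every visit. The Protocol 1.3 footnote lists it as "dipstick [pH, specific gravity, protein, glucose, ketones, bilirubin, blood, urobilinogen, and leukocyte esterase". SAP 7.4 shows how the blood result is recorded: "Hematuria (Urine Blood/Hgb values of “Trace”, ‘1+’, ‘2+’, ‘3+’, ‘Present’, etc". Glucose is recorded in the same way.

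SAP 9.5.1 plans low-normal-high shift tables for hematology, serum chemistry, quantitative urinalysis and lipids. For the remaining urinalysis parameters it plans one display: "a shift table depicting shifts to/from positive/negative from baseline to worst and last value will be provided". It does not say whether Trace counts as positive.

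These tables serve a stated safety endpoint (SAP 3.2.2): "Changes from baseline in body weight, vital signs, physical examinations, peripheral edema, and clinical laboratory parameters". For peripheral edema, another ordinal measure, SAP 9.7.1 keeps all grades from 0 to 4+ in its shift to worst and last value.

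**The concern.** Cutting an ordered scale at one point discards every change that stays on the same side of the cut. A participant who starts positive for blood has one way to move in the planned table, which is to become negative. An increase in grade has no cell, and neither does a decrease that stops short of negative.

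Urine blood is the analyte for which this matters most. Protocol section 2 describes the target population as having "persistent proteinuria that may be accompanied by microscopic hematuria", so some participants can be expected to start positive. A 24-week safety summary that cannot show whether their hematuria rose or partly fell gives an incomplete account of change from baseline for that parameter.

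**Working it through.** The plan gives no figure on this point. Its only design calculation (SAP 4.3.1) is the chance of seeing at least one adverse event: 1 − 0.95^60 = 0.954, which agrees with the stated 95%. It does not enter here.

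**Step 1: what the two-category table can show.** Take the ordered levels negative, Trace, 1+, 2+, 3+ from SAP 7.4, leaving Present aside because it has no rank. The number of distinct upward moves is 5 × 4 / 2 = 10. A move is visible only if it crosses the positive/negative cut.

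| | Trace counted positive | Trace counted negative |
|---|---|---|
| Upward moves visible | 1 × 4 = 4 of 10 | 2 × 3 = 6 of 10 |
| Upward moves from a positive baseline | 4 × 3 / 2 = 6 | 3 × 2 / 2 = 3 |
| Of these, visible | 0 | 0 |

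Downward moves mirror this. From a positive baseline, complete clearance is visible, and the 6 (or 3) partial improvements are not. These are counts of possible moves, not probabilities. A graded table would show all 10 moves in each direction.

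**Step 2: worst value and last value.** The restriction on worsening is the same in both tables. Both can show clearance: a participant positive at baseline whose later results are all negative has a negative worst value as well as a negative last value.

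**Step 3: whether another planned summary covers urine blood.**

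- *Descriptive statistics, SAP 9.5:* these are for quantitative results, so dipstick grades are outside them. They also explain why the low-normal-high tables matter less: for those analytes, movement within the high range still appears in the summaries of change.
- *Quantitative urinalysis, SAP 8.2.3.1:* "Quantitative urinalysis parameters (protein excretion, albumin excretion, urea, and creatinine". Protocol 10.3, Table 4, agrees and lists no microscopy or red-cell count. Blood appears there only under routine urinalysis.
- *CTCAE shifts, SAP 9.5.2:* these cover laboratory tests that are not named, and no rule is given for grading dipstick blood.
- *Adverse events:* Protocol 8.4.4 has the investigator record clinically significant changes. Protocol 10.5.1 includes urinalysis results that worsen when judged significant, but leaves out findings tied to the underlying disease unless they are more severe than expected.
- *Listings, Protocol 9.3.3 and SAP 6.1:* individual values appear, but they are not summarized.

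**Step 4: how many participants this could touch.** The documents give no baseline hematuria rate. Purely as assumptions, with 60 participants:

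| Assumed share positive for blood at baseline | No cell for worsening | Can show worsening |
|---|---|---|
| 25% | 60 × 0.25 = 15 | 45 |
| 50% | 60 × 0.50 = 30 | 30 |
| 75% | 60 × 0.75 = 45 | 15 |
| 90% | 60 × 0.90 = 54 | 6 |

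**The case against.** The best defense is that this is a display preference with low stakes. The study is single-arm, exploratory and descriptive, with no hypothesis (Protocol 9.1 and 9.3.3). Hematuria is not a named endpoint, not among the safety topics in SAP 9.1.2, and not in the risk table in Protocol 2.3.1. Edema, the comparison used here, is a named endpoint tied to a known risk, so fuller tabulation there is easier to justify. A five-by-five table with about 60 participants will have many empty cells. All of this stands, and it keeps the point small. It does not supply the missing summary: the parameter falls under a stated safety endpoint, and the graded data are already collected.

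A reader might go further and infer that worsening hematuria could never come to light in this study. The documents do not support that. Listings carry every value, and an investigator can report a significant change as an adverse event. The limitation belongs to the shift tables.

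A reader might also infer that the informative cells are nearly empty because almost everyone starts positive. The entry criterion "Participant has a UA/C ≥ 0.3 g/g at screening" bears on protein, and SGLT2 inhibitor use bears on glucose (an inference, not a statement in the documents). Neither says anything about blood, and Protocol section 2 says only that hematuria may be present. For protein, UA/C and UP/C give quantitative measures, so little is lost. Expressing the loss as statistical power would not help either: it needs a grade distribution that the documents do not give and a test that nobody plans.

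**Conclusion.** The point holds as a reporting gap in one safety display. In the tables planned in SAP 9.5.1, a participant positive for urine blood at baseline cannot show worsening or partial improvement, wherever the cut for Trace falls. No other planned tabulation clearly shows it. This follows from the structure of the table and rests on one reading: that the positive/negative sentence governs dipstick blood. SAP 9.5.1 supports that reading, since quantitative urinalysis is dealt with separately in the sentence before.

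The number of participants affected is unknown, because it depends on an undocumented baseline rate. The primary analysis and the other efficacy analyses are unaffected. This is a cheap improvement, not an error that threatens a conclusion.

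**What to change.** In SAP 9.5.1, for urine blood, replace the positive/negative shift with a shift by grade (negative, trace, 1+, 2+, 3+ or more) from baseline to worst and to last value, in the layout of SAP 9.7.1. Put ungraded Present results in a separate category, since they cannot be ranked against the grades. Other graded dipstick analytes can follow the same format, but this is optional. If a positive/negative table is also shown, state whether Trace counts as positive. SAP 7.4 lists Trace among the hematuria values, but SAP 9.5.1 does not carry that over.

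The cost is a few lines of SAP text and a larger table shell. No new data are needed. The downside is sparser cells at about 60 participants. This is tolerable in a descriptive table, because grades can be collapsed afterwards, whereas a positive/negative table cannot be expanded.

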### **9.5.2. Shifts in Common Terminology Criteria for Adverse Events Toxicity Grade**

Shifts in Common Terminology Criteria for Adverse Events (CTCAE) toxicity grade of laboratory tests from baseline to worst value (including scheduled or unscheduled) and last value including scheduled and unscheduled will be provided. Results will be attributed to a grade based on CTCAE version 5.

Summaries will present the number and percentage of patients with shifts in laboratory toxicity grade.

### **9.5.3. Incidence of Liver Function Abnormalities**

The incidence of patients (number and percentage of patients) with abnormalities in liver function tests (ALT, AST, alkaline phosphatase [ALP], and total bilirubin) post-baseline during the study will be summarized for the following categories:

- ALT and AST:
  - $>1 \times \text{ULN}$
  - $>2 \times \text{ULN}$
  - $>3 \times \text{ULN}$
  - $>5 \times \text{ULN}$
  - $>8 \times \text{ULN}$
- ALP:
  - $>1 \times \text{ULN}$
  - $>1.5 \times \text{ULN}$
  - $>2.5 \times \text{ULN}$
  - $>5 \times \text{ULN}$

- Total bilirubin:
  - $>1 \times \text{ULN}$
  - $>1.5 \times \text{ULN}$
  - $>2 \times \text{ULN}$
  - $>3 \times \text{ULN}$

Scatterplots of ALT vs AST, ALT vs total bilirubin, and AST vs total bilirubin maximum post-baseline values occurring during the study will be presented. If appropriate, evaluation of drug-induced serious hepatotoxicity plots of ALT or AST  $>3 \times \text{ULN}$  accompanied with total bilirubin by treatment group will be presented for assessment of potential drug induced liver injury. A listing of patients with  $>2 \times \text{ULN}$  total and  $>3 \times \text{ULN}$  ALT or AST at any time during the study will be provided.

#### **9.5.4. Incidence of N-Terminal Prohormone of Brain Natriuretic Peptide Elevations**

The incidence of patients (number and percentage of patients) with abnormalities N-terminal prohormone of brain natriuretic peptide (NT-proBNP) during the study will be summarized for the following categories:

- Patients with NT-proBNP  $> \text{ULN}$  post-baseline
- Patients with NT-proBNP  $> \text{ULN}$  pre- and post-baseline
- Patients with NT-proBNP  $>47 \text{ pmol/L}$
- Patients with NT-proBNP  $>142 \text{ pmol/L}$

The denominator will be the number of patients with at least 1 post-baseline result during the study. Patients who do not have a baseline value will be considered to be within the normal range at baseline.

#### **9.6. Vital Signs**

The results and change from baseline at each post-baseline scheduled visit will be summarized for BP (systolic and diastolic), heart rate, respiration rate, temperature, and body weight.

The number and percentage of patients meeting the following criteria at any time during the study will also be summarized:

- Systolic BP:
  - $\leq 100 \text{ mmHg}$
  - A decrease from baseline more than 30 mmHg
  - $>180 \text{ mmHg}$
  - An increase from baseline more than 40 mmHg

- Diastolic BP:
  - $\leq 60$  mmHg
  - A decrease from baseline more than 20 mmHg
  - $> 105$  mmHg
  - An increase from baseline more than 20 mmHg
- Heart rate:
  - $< 45$  beats per minute
  - A decrease from baseline more than 20 beats per minute
  - $> 120$  beats per minute
  - An increase from baseline more than 20 beats per minute

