1.3. Schedule of Activities (SoA)

| | Screening | Baseline | Study Treatment Period | | | | Safety Follow-up Visit |
|--|---|----------|------------------------|----------|----------|-----------------|-----------------------------|
| Week | -- | Day 1 | Week 2 | Week 4 | Week 12 | Week 24/ EOT | Week 28/4-week Safety Visit |
| Visit | 1 | 2 | 3 | 4 | 5 | 6 | 7 |
| Visit Window | Day -42 to Day -1 | -- | ± 5 days | ± 7 days | ± 7 days | ± 7 days | ± 7 days |
| Informed Consent | X | | | | | | |
| Inclusion/Exclusion | X | | | | | | |
| Screening Tests ^a | X | | | | | | |
| IRT | X | X | | | | | |
| Medical History | X | | | | | | |
| Demographics | X | | | | | | |
| Peripheral Edema Assessment ^b | X | X | X | X | X | X | X |
| Vital Signs ^c | X | X | X | X | X | X | X |
| Clinical Laboratory Assessments ^d | X | X | X | X | X | X | X |
| Lipid Panel ^e | X | X | | | X | X | |
| Physical Examination ^f | X | X | X | X | X | X | X |
| Adverse Event Assessment | -----Continuous Monitoring----- | | | | | | |
| Concomitant Medications/Therapies | -----3 Months prior to screening followed by Continuous Monitoring----- | | | | | | |
| RAAS Inhibitor Treatment ^g | X | | | | | X | |
| SGLT2 Inhibitor Treatment | -----Continuous Treatment----- | | | | | | |
| Quantitative urinalysis | X | X | | X | X | X | X |
| Calculate eGFR ^h | X | X | X | X | X | X | X |
| Study Intervention Dispensing | | X | X | X | X | | |
| Study Intervention Accountability | | | X | X | X | X | |
| Pregnancy Test ⁱ | X | X | X | X | X | X | X |
| Dispense Urine Pregnancy Test ^j | | | | X | X | | |

Abbreviations: ALP = alkaline phosphatase; ALT = alanine transaminase; AST = aspartate aminotransferase; BP = blood pressure; BUN = blood urea nitrogen; eGFR = estimated glomerular filtration rate; EOT = end of treatment;

HDL = high-density lipoprotein; IRT = interactive response technology system; LDL = low-density lipoprotein; MCH = mean corpuscular hemoglobin; MCHC = mean corpuscular hemoglobin concentration; MCV = mean corpuscular volume; pH = potential for hydrogen; RAAS = renin-angiotensin-aldosterone system; SOC = standard of care; SGLT2 = sodium glucose cotransporter-2; WBC = white blood cell.

- a Includes plasma follicle stimulating hormone level (to confirm menopausal status only).
- b Peripheral edema assessment guidance provided in [Section 10.4](#).

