| Transaminase elevations. | Elevations of aspartate aminotransferase (AST) or alanine aminotransferase (ALT) greater than 3x upper limit of normal (ULN) have been observed in studies of sparsentan, though concurrent elevation of bilirubin has not been observed. | Sparsentan can be discontinued in participants with clinically relevant aminotransferase elevations or if aminotransferase elevation is accompanied by a greater than 2x ULN increase in bilirubin or by clinical symptoms of hepatotoxicity. |
| Hyperkalemia. | Participants with advanced kidney disease or taking concomitant potassium-increasing drugs are at increased risk for hyperkalemia. | Potassium will be monitored at each visit for clinical evidence of electrolyte imbalance, with the course of action dependent on the potassium level and likely cause of increase. Management includes modifications in diet, diuretics, or potassium lowering medications. Sparsentan can be held or discontinued in participants who develop clinically significant hyperkalemia. |
| AKI. | Changes in kidney function and impaired kidney function can be caused by drugs that inhibit the RAAS system. Participants with renal artery stenosis, CKD, severe CHF, or volume depletion may be at particular risk of developing clinically significant AKI. The combination of sparsentan and SGLT2 inhibitors may enhance the risk of AKI. | Kidney function will be monitored periodically in this clinical study. Sparsentan can be held or discontinued in participants who develop clinically significant disease. |

Table 1: Risk Assessment (Continued)

| Identified/Potential Risk of Clinical Significance | Summary of Data/Rationale for Risk | Mitigation Strategy |
|--|---|---|
| Hypotension. | Hypotension has been observed in patients treated with ARBs and ERAs and has been observed in clinical studies of sparsentan. The combination of sparsentan and SGLT2 inhibitors may enhance the risk of hypotension. | In patients at risk for hypotension, consider eliminating or adjusting other anti-hypertensive medications. If hypotension develops despite elimination or reduction of other anti-hypertensive medications, the dose of sparsentan can be reduced or interrupted. |

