## 4. STUDY DESIGN

### 4.1. Summary of Study Design

This is a 28-week, open-label, multicenter, single-group, Phase 2 exploratory study to determine the safety and effect of sparsentan in participants with IgAN who are at risk of disease progression despite being on both stable renin-angiotensin-aldosterone system inhibitor (RAASi) and SGLT2 inhibitor treatment for at least 12 weeks prior to study entry.

Approximately 60 participants aged  $\geq 18$  years will be enrolled into this study.

[figure not shown]
Participants who provide written informed consent will be assessed for eligibility and will undergo baseline evaluations including clinical laboratory tests. Per the eligibility criteria, all participants are required to be on a stable dose(s) of angiotensin converting enzyme inhibitor (ACEI) and/or angiotensin receptor blocker (ARB) and on a stable dose of a SGLT2 inhibitor at screening and will continue their stable treatments through the screening period. Eligible participants entering the study will remain on the stable dose of the SGLT2 inhibitor for the duration of the study, however, they will discontinue ACEI and/or ARB therapy before the Day 1 visit. The final dose of an ACEI and/or ARB should be taken on the day before the Day 1 visit. Baseline evaluations will be taken on Day 1 prior to administration of the first dose of the study medication (sparsentan).

Study medication will be administered daily for a treatment period of 24 weeks with study visits conducted at weeks 2-, 4-, 12-, and 24- following Day 1. Following the 24-week treatment period, study medication will be discontinued for 4 weeks. At this time, the Investigator should resume standard of care treatment, including RAASi treatment. Participants will return to the site for a visit at Week 28 for the safety follow-up visit.

UA/C and UP/C will be determined using first morning void (FMV) samples and will be calculated as the average of 2 FMV samples collected within 3 days prior to each visit. If 1 of the samples is missing, UA/C and UP/C from the single sample will be used.

The overall study design is summarized in Figure 1 (below). For individual participants, the total duration of participation from the screening visit to the safety follow-up visit (Week 28) will be a maximum 34 weeks.

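### SAP 9.6 sets no post-baseline or on-treatment limit for the vital-sign threshold counts, so off-drug Week 28 values are counted and pre-dose values are not excluded from the absolute thresholds

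*SAP*

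**What the plan says.** SAP 9.6 has two parts. The first covers by-visit summaries: "The results and change from baseline at each post-baseline scheduled visit will be summarized for BP (systolic and diastolic", with heart rate, respiration rate, temperature and weight also listed. The second adds a threshold table: "The number and percentage of patients meeting the following criteria at any time during the study will also be summarized". That table has 12 criteria, four each for systolic BP, diastolic BP and heart rate. Six are absolute levels (systolic ≤100 or >180 mmHg, diastolic ≤60 or >105 mmHg, heart rate <45 or >120 beats per minute). The other six are rises or falls from baseline.

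The schedule in Protocol 1.3 marks vital signs at all seven visits: "Vital Signs ^c | X | X | X | X | X | X | X". These are screening, Day 1, Weeks 2, 4, 12 and 24, and Week 28. SAP 4.1 places Day 1 before dosing: "Baseline evaluations will be taken on Day 1 prior to administration of the first dose of the study medication (sparsentan". It places Week 28 off drug: "Following the 24-week treatment period, study medication will be discontinued for 4 weeks", and "At this time, the Investigator should resume standard of care treatment, including RAASi treatment".

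Other parts of the SAP do set a window or show baseline status. The liver table in 9.5.3 counts abnormalities "post-baseline during the study will be summarized for the following categories". Section 9.5.4 separates NT-proBNP elevations that are post-baseline from those both pre- and post-baseline. Section 9.7.1 gives edema a shift table from baseline. Section 9.1 restricts adverse event summaries to events that start or worsen after dosing begins, within the treatment period.

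**The concern.** Protocol Table 1 names low blood pressure as a risk of the combination: "The combination of sparsentan and SGLT2 inhibitors may enhance the risk of hypotension". The SAP 9.6 table is the only planned summary that counts participants against blood pressure thresholds. Its low cut-offs are also the levels at which Protocol 6.6 holds participants at the starting dose.

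Protocol 5.1 sets upper but no lower blood pressure limits. It also requires maximum tolerated ACEI and/or ARB plus a stable SGLT2 inhibitor. Some participants may therefore meet a low threshold before any sparsentan. Nothing in the 9.6 table would distinguish them from participants who first met it on sparsentan, and there is no control arm to show the background rate.

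The table's window also differs from the one for hypotension-associated adverse events (SAP 9.1.2 under the 9.1 definition), so the two displays of the same risk would not cover the same period.

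**Working it through.** The plan gives no figure for this table. Its one computed figure, a 95% chance of seeing at least one event of 5% incidence in 60 participants, reproduces (1 − 0.95^60 = 0.954) but does not bear on this point.

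**Step 1: visits that can trigger a criterion.** Two visits are pre-dose (screening, Day 1), four are in the treatment period (Weeks 2, 4, 12, 24) and one is off drug (Week 28). An absolute threshold can be triggered at 7 scheduled visits on the literal wording, 5 if limited to post-baseline, and 4 if limited to treatment. Participants who stop early also have a safety visit about 4 weeks after the last dose (Protocol 7.1), which is likewise off drug.

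**Step 2: which criteria are affected.** SAP 6.5.2 defines change as post-baseline minus baseline, so pre-dose values cannot meet the six change criteria. Only off-drug values can add to those. Pre-dose values can reach the six absolute thresholds, with one limit: Protocol 5.1 requires screening systolic ≤160 and diastolic ≤110 mmHg. An eligible screening systolic value therefore cannot exceed 180, and an eligible screening diastolic value can exceed 105 only between 105 and 110.

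**Step 3: size for the two low-BP thresholds.** Assumed inputs, since the documents give none: diastolic mean 76 to 80 mmHg, SD 9 to 10; systolic mean 122 to 130 mmHg, SD 13 to 14; normal values; correlation 0.6 between any two visits; the same distribution at all seven visits (no drug effect). With z = (threshold − mean)/SD, the chance of meeting the threshold at least once in m visits is

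P(m) = 1 − ∫ φ(u) · [1 − Φ((z − √0.6·u)/√0.4)]^m du.

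Participants counted only because of pre-dose values are P(6) − P(4). Those counted only because of pre-dose or Week 28 values are P(7) − P(4). Results in percent, with differences taken before rounding:

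| Mean/SD | P(2), pre-dose alone | P(4) | P(6) | P(7) | P(6)−P(4) | P(7)−P(4) |
|---|---|---|---|---|---|---|
| Diastolic 76/9 | 6.47 | 10.39 | 13.25 | 14.44 | 2.86 | 4.06 |
| Diastolic 76/10 | 9.21 | 14.38 | 18.04 | 19.53 | 3.65 | 5.15 |
| Diastolic 80/9 | 2.36 | 4.01 | 5.32 | 5.89 | 1.31 | 1.88 |
| Diastolic 80/10 | 4.00 | 6.62 | 8.61 | 9.46 | 2.00 | 2.85 |
| Systolic 122/13 | 7.70 | 12.19 | 15.43 | 16.76 | 3.23 | 4.57 |
| Systolic 122/14 | 9.72 | 15.11 | 18.90 | 20.44 | 3.79 | 5.33 |
| Systolic 130/13 | 1.90 | 3.27 | 4.36 | 4.84 | 1.10 | 1.58 |
| Systolic 130/14 | 2.86 | 4.82 | 6.36 | 7.02 | 1.53 | 2.20 |

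The net excess from pre-dose values is 1.1% to 3.8%, or 0.7 to 2.3 of 60. With Week 28 it is 1.6% to 5.3%, or 0.9 to 3.2 of 60. The gross P(2) column, 1.9% to 9.7%, is larger because many of those participants would also qualify at a treatment visit.

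**Step 4: sensitivity.** If the mean at the four treatment visits is 4 mmHg lower (an assumption) and Week 28 returns to the pre-dose level, the net excess falls to 0.7% to 2.3% from pre-dose values, and to 1.0% to 3.3% with Week 28.

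**The case against.** The strongest reply is that the threshold sentence follows one limited to post-baseline visits, and its use of *also* may carry that limit over. A reader might infer that pre-dose values will certainly be tallied. The documents do not settle that: inclusion is the literal reading, not an explicit instruction. The ambiguity remains, because the second sentence replaces the visit limit with a whole-study period, and 9.5.3 shows that the SAP adds the post-baseline qualifier when it wants it.

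A reader might also infer that the problem would be invisible, or that low values would be attributed to sparsentan. Neither follows. Baseline BP is tabulated (SAP 7.4), BP is summarized by visit so Week 28 appears on its own, the fall-from-baseline criteria cannot be met pre-dose, by-patient listings are planned (SAP 6.1), and hypotension adverse events have their own window. The table is a descriptive count and asserts no cause.

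Nor is counting Week 28 an error in itself, since it is the planned safety follow-up visit. The liver table would include it too, so that comparison supports only the pre-dose half. What stands is that the threshold table mixes on-drug and off-drug values without showing which are which.

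**Conclusion.** The point holds as an unspecified counting window. Off-drug values enter all 12 criteria, and pre-dose values are not excluded from the six absolute thresholds. The table therefore cannot show how many participants newly met a low-BP threshold on sparsentan.

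The size is small: about 1 to 2 of 60 participants from pre-dose values, and about 1 to 3 of 60 with Week 28. These rest wholly on assumed means, SDs, correlation and normality. It would be tempting to take the gross pre-dose rate as the distortion, but that overstates it, because only participants not counted at a treatment visit add to the total.

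Severity is minor: the study is exploratory, single-arm and descriptive, and other planned outputs let a reader recover the information.

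**What to change.** In SAP 9.6, replace the any-time wording with: *at any post-baseline assessment after the first dose during the treatment period*, and state a cut-off in days after the last dose. The 3-day rule in SAP 8.1 is written for efficacy analyses. It is one option for the cut-off, but adopting it here would be a choice. Adding only a post-baseline qualifier would settle the pre-dose half and leave Week 28 mixed in.

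Show each absolute criterion by whether it was already met at baseline, as 9.5.4 and 9.7.1 do for NT-proBNP and edema. Report Week 28 and other off-treatment values in a separate row, so that the safety follow-up is kept.

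The cost is SAP wording and table-shell edits, with somewhat lower headline counts. No new data are needed.
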